 - Patients with ≤PR at completion of 4 cycles, will stop therapy and be taken off protocol at completion of 4 cycles.

- For patients achieving >PR at end of 4 cycles, patients will continue to receive combination therapy with maximum up to 12 cycles.
 - Patients obtaining CR/sCR at any point during cycles in serum and urine will undergo MRD testing using multi-parametric flow cytometry.
 - Patients who attain minimal residual disease (MRD) negative status will stop treatment after 2 additional cycles (maximum 12 cycles).
 - Patients who are MRD positive will stop treatment at completion of 12 cycles. Patients converting from MRD positive status to negative status on subsequent MRD testing can stop after 2 additional cycles
 - Patients achieving <CR/sCR (and >PR at end of 4 cycles) will stop treatment at completion of 12 cycles.
- Upon completion of protocol therapy, patients will be encouraged to proceed onto maintenance therapy or high dose therapy with stem cell rescue under a separate treatment protocol or standard of care. If clinically indicated, patients may need alternative therapy.
- After completion of protocol therapy, patients will remain on study for an additional 3 years for survival analysis.

[figure not shown]
Treatment Plan (see schema below)

- Cycle 1 ONLY: Carfilzomib 20 mg/m² per dose, days 1 and 2; Carfilzomib 45 or 56 mg/m² per dose, days 8, 9, 15, and 16
- Cycles 2- up to 12: Carfilzomib 45 or 56 mg/m² per dose, days 1, 2, 8, 9, 15, and 16
- Cycles 1- up to 12: Lenalidomide 25 mg/day, days 1–21 every 28 days
- Cycles 1-4: Dexamethasone 20 mg/dose, days 1, 2, 8, 9, 15, 16, 22, and 23
- Cycles 5- up to 12: Dexamethasone 10 mg/dose, days 1, 2, 8, 9, 15, 16, 22 and 23
- After receiving first 4 cycles, patients who are considered to be eligible for subsequent high dose therapy/autologous stem cell transplant (ASCT) will undergo autologous stem cell harvesting for potential use in the future. For patients who choose to undergo stem cell harvest, next cycle may be delayed for up to 7 weeks.
- If patients achieve > PR after completion 4 cycles, patients may receive additional combination therapy (maximum permissible 12 cycles). Patients may go onto receiving additional maintenance phase therapy with lenalidomide under a separate treatment protocol.
 - Patients obtaining CR/sCR and MRD negative status by flow cytometry will stop treatment after 2 additional cycles (maximum 12 cycles) delivered.

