13.0 CRITERIA FOR REMOVAL FROM STUDY

Off-therapy Criteria

Patients with medically concerning grade 3 or 4 adverse events related to drug therapy may be taken off therapy at the discretion of the principal investigator.

- Patients who require more than 2 dose reductions of carfilzomib
- Hematologic toxicity has not completely resolved or resolved to < grade 1 or baseline after 2 weeks of withholding treatment
- Therapy has been held for more than 3 weeks due to treating a grade 3 infection
- Grade 4 non-blistering rash or blistering rash of any grade
- Grade 4 neuropathy
- Grade 4 hypersensitivity reaction
- Patient experiencing significant cardiac event as outlined in section 9.5

- Patient completes the protocol treatment
- Progression of disease
- Patient chooses to go off therapy
- The principal investigator may remove patient from protocol therapy if deemed necessary due to medical conditions, compliance, etc.
- Patient becomes pregnant.

Off-Study Criteria

- Patient requests to be withdrawn from study
- Death
- Physician's determination that withdrawal is in the patient's best interest.

Patient has completed 1- and 3-year evaluation from end of therapy

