The phase II component of this trial will explore the efficacy of the combination therapy using the carfilzomib dose selected in the phase I trial. The primary endpoint is CR/sCR MRD negativity (MRD-) rate by flow cytometry upon or prior to completion of 12 cycles of therapy. Patients with <CR/sCR are considered MRD positive. Based on previous research an CR/sCR MRD- rate by flow cytometry of 45% would be promising enough to warrant further investigation, while a rate of 20% would not be promising for further investigation. Using a Simon's optimal two-stage design, the first stage of the trial will enroll 14 patients. This includes the three-six patients treated at the MTD in the phase I trial. If three patients or fewer are CR/sCR MRD- by flow cytometry, the trial will stop due to a lack of efficacy; otherwise, an additional 11 will enroll to a total sample size of 25 at end of phase II. If at least eight patients are MRD- (at the MTD), the intervention will be considered promising for further research. The type I error is set at 0.10 and the type II error is set at 0.10. If the true MRD-rate is 20%, the probability of early termination is 70%. For patients that come off trial prior to completion of 4 cycles of therapy, due to reasons unrelated to disease progression or toxicities, patients can be replaced (max 3) for MRD evaluation as part of the phase II assessment.

It is anticipated that 1-2 patients per month may enroll on this trial; thus, approximately one year is anticipated as the accrual period for the phase II study. The total maximum possible projected sample size for the study is 37 patients.

Secondary endpoints for both Phase I and II:

1. To estimate the overall response rate (ORR) according to International Myeloma Working Group criteria at each cycle and as the best response during the treatment of up to 12 cycles. In addition to ORR, the rates of VGPR+CR and CR alone will also be estimated and reported. The exact 95% confidence intervals will also be included.
2. Kaplan-Meier methodology will be used to estimate progression-free survival and overall survival. Estimates of survival along be with 95% confidence intervals will be provided for select time points.

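### Optional replacement of up to three early leavers can bias the MRD-negative rate and the 8-of-25 decision upward if leaving is related to response, and no all-treated result is planned.

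*Combined protocol and SAP*

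**What the plan says.** Section 14.0 (Phase II) makes the primary endpoint CR/sCR with MRD negativity by flow cytometry, reached at or before the end of 12 cycles. It adds: "Patients with <CR/sCR are considered MRD positive". The design is: "Using a Simon's optimal two-stage design, the first stage of the trial will enroll 14 patients". The trial stops if three or fewer of these 14 succeed. Otherwise 11 more enrol, and at least 8 successes among 25 make the regimen promising. The null planning rate is 20% and the target is 45%: "an CR/sCR MRD- rate by flow cytometry of 45% would be promising enough to warrant further investigation". On error rates: "The type I error is set at 0.10 and the type II error is set at 0.10".

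The same paragraph then provides for patients who come off trial before completing 4 cycles: "due to reasons unrelated to disease progression or toxicities, patients can be replaced (max 3) for MRD evaluation". It does not say who decides, whether response may be considered, or whether a replaced patient stays in any denominator. Section 14.0 plans no analysis of all patients treated at the selected dose.

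Two other places bear on who can leave early. Section 13.0 lists "Patient chooses to go off therapy" among the off-therapy criteria and also lets the principal investigator remove a patient for open-ended reasons. Section 1.0 sets the planned exit of poor responders: "Patients with ≤PR at completion of 4 cycles, will stop therapy".

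**The concern.** Under the endpoint definition, a patient who leaves without reaching CR/sCR is a failure. The replacement rule allows up to three such patients to be left out of the 25 and substituted. Three features make it possible for this to depend on outcome.

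- Only progression and toxicity are barred as reasons. Inadequate response short of progression is not. A patient in stable disease or PR who leaves by choice after cycle 3 is replaceable. The same patient at completion of cycle 4 is stopped for response of PR or worse and counts as a failure.
- Replacement is permitted, not required, in a single-arm trial. Section 1.0 has response evaluated monthly, so response is known when the choice is made.
- Patients who leave before cycle 4 will mostly not be in CR. Section 3.1 reports a median of 5 cycles to sCR (range 2 to 18) in the earlier CRd study.

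At stake is what the primary rate describes. If failures can leave the denominator, x/25 is no longer the rate among patients who started treatment at the selected dose, and the stated type I error does not apply to that all-treated rate. With 25 patients and a cut-off of 8, a few replacements can change the call.

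**Working it through.** **Inputs from Section 14.0.** Null rate 0.20; promising rate 0.45; n1 = 14, stop if 3 or fewer; n = 25, promising if 8 or more; at most 3 replacements. **Assumed, because the documents give no figure:** the probability q that a patient is a replaceable early leaver, taken from 0 to 20%.

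**Step 1. Reproduce the design without replacement.** With X1 ~ Bin(14, p) and X2 ~ Bin(11, p), P(promising) = sum over x from 4 to 14 of P(X1 = x) × P(X2 ≥ 8 − x). At p = 0.20:

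| Stage 1 successes x | P(X1 = x) | P(X2 ≥ 8 − x) | Product |
|---|---|---|---|
| 4 | 0.1720 | 0.1611 | 0.0277 |
| 5 | 0.0860 | 0.3826 | 0.0329 |
| 6 | 0.0322 | 0.6779 | 0.0219 |
| 7 | 0.0092 | 0.9141 | 0.0084 |
| 8 or more | 0.0024 | 1 | 0.0024 |
| Sum | | | 0.0933 |

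Power at p = 0.45 is 0.903. Early termination at p = 0.20 is P(X1 ≤ 3) = 0.698. These agree with the stated limits of 0.10 and 0.10 and the stated 70%.

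**Step 2. Add the replacement rule, leavers all non-CR.** Each enrolled patient is a success (probability p), a replaceable leaver (q) or another failure (1 − p − q). Let f(c, s, k) be the probability of ending promising with c patients counted, s successes and k replacements used. Then

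f(c, s, k) = p·f(c+1, s+1, k) + (1 − p − q)·f(c+1, s, k) + q·L,

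where L = f(c, s, k+1) if k < 3 and L = f(c+1, s, k) if k = 3. The boundaries are f = 0 at c = 14 with s ≤ 3, and at c = 25 f = 1 if s ≥ 8, otherwise 0. The all-treated rate is held at p = 0.20.

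**Step 3. The contrasting case: leaving unrelated to response.** The same recursion is used, but the 20% rate now applies to patients who stay, so p = 0.20 × (1 − q).

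| q | Step 2: leavers all non-CR, replaced | Same, no replacement | Step 3: leaving unrelated to response, replaced |
|---|---|---|---|
| 0 | 0.093 | 0.093 | 0.093 |
| 2% | 0.102 | 0.093 | 0.093 |
| 4% | 0.112 | 0.093 | 0.093 |
| 8% | 0.130 | 0.093 | 0.089 |
| 10% | 0.138 | 0.093 | 0.086 |
| 10.7% | 0.141 | 0.093 | 0.084 |
| 20% | 0.160 | 0.093 | 0.058 |

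The ceiling under Step 2 arises when all three replacements are used before the stage 1 look. The rule then amounts to more than 3 of 17 followed by at least 8 of 28, which gives 0.167.

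**Step 4. The estimate at the boundary.** 8/25 = 32.0% (exact 95% CI 14.9 to 53.5%). With three replaced patients restored as failures, 8/(25 + 3) = 8/28 = 28.6% (13.2 to 48.7%). The difference is 3.4 percentage points.

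**The case against.** The plan already keeps the exits most clearly tied to outcome. Leavers for progression or toxicity cannot be replaced. The planned removal of patients at PR or worse falls at completion of cycle 4, outside the window, so those patients stay as failures. The cap of three bounds any distortion. All of this stands, and it limits the gap to poor responders without progression who leave before completing 4 cycles by patient or investigator choice.

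A capped evaluable population is also a legitimate target. If leaving has nothing to do with response, replacement does not inflate the error, as the last column of the table shows. This stands too, but the plan contains nothing that would let a reader tell which situation applies.

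There is also an ambiguity. The replacement rule speaks of coming off trial, while patient choice is listed in Section 13.0 under off-therapy criteria, and patients remain on study for three years after therapy. The off-study list also allows withdrawal by patient request or physician judgement, so the gap is open on either reading.

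A reader might infer that the rule removes only non-CR leavers and keeps every success, so that the primary rate is necessarily biased upward. The text does not say this. It sets no response condition, and read literally an early success who came off before 4 cycles could also be replaced. Selective use is possible under the rule but is not written into it.

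**Conclusion.** The point holds in conditional form. Section 14.0 leaves an optional, response-visible replacement unguarded and plans no analysis that restores the replaced patients. Relative to all patients treated at the selected dose, the MRD-negative rate and the 8-of-25 decision can be biased upward if early leaving is related to response.

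If the all-treated rate is 20% and replaced leavers are all non-CR, the false-positive probability goes from 0.093 to about 0.10 at 2% replaceable leavers, 0.14 at 10 to 11% and 0.16 at 20%. The boundary estimate shifts by at most 3.4 points. If leaving is unrelated to response, the probability is 0.093 or lower. Every inflated figure rests on an assumed leaving rate, so the documents do not support a statement that the type I error is exceeded, only that it can be. Confidence is moderate. The change is worth making because it is cheap and the decision rests on 25 patients.

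**What to change.** In Section 14.0:

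1. State that the MRD-negative rate, with its exact confidence interval, will also be reported for every patient who received at least one dose at the selected dose level. Early leavers without documented CR/sCR MRD negativity count as not MRD-negative. A patient who reached it before leaving counts as a success.
2. Require any conclusion that the regimen is promising to show this all-treated result (x of up to 28) beside the x/25 result.
3. State that the decision to replace a patient is made without regard to response status.

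The cost is one paragraph in Section 14.0 and one extra line in the results, with no new patients or procedures. The downside is a slightly less favourable reported rate if replacements occur. Making replacement automatic, or limiting it to exits before any response assessment, is a further design choice that this point does not require.

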15.0 RESEARCH PARTICIPANT REGISTRATION AND RANDOMIZATION PROCEDURES

15.1 Research Participant Registration

Confirm eligibility as defined in the section entitled Inclusion/Exclusion Criteria. Obtain informed consent, by following procedures defined in section entitled Informed Consent Procedures. During the registration process registering individuals will be required to complete a protocol specific Eligibility Checklist. The individual signing the Eligibility Checklist is confirming whether or not the participant is eligible to enroll in the study. Study staff are responsible for ensuring that all institutional requirements necessary to enroll a participant to the study have been completed. See related Clinical Research Policy and Procedure #401 (Protocol Participant Registration).

15.2 Randomization

This study will not include randomization.

16.0 DATA MANAGEMENT ISSUES

All patients will be enrolled on protocol at Memorial Sloan-Kettering Cancer Center. We expect to be able to enroll the necessary 34 patients into this study in 2 years.

The data manager (Clinical Research Coordinator/CRC) will be responsible for confirming eligibility and assisting the MD with the registration process. All study data will be collected by an assigned CRC who will enter this information into the Clinical Research Database (CRDB). This database will be utilized for data collection and storage and for reporting protocol specific events such as accrual demographics, toxicities and adverse events to the IRB, and the sponsor.

The CRC will collect toxicity and concomitant medication information and patient interviews. Adverse events, including all toxic effects of treatment will be tabulated individually according to severity or toxicity grade. The data manager will also monitor laboratory testing throughout

the study. Laboratory data will be tabulated and summarized by descriptive statistics, as well as on the basis of MSKCC specified normal ranges.

16.1 Quality Assurance

Monthly registration reports will be generated to monitor patient accruals and completeness of registration data. Routine data quality reports will be generated to assess missing data and inconsistencies. Accrual rates, extent and accuracy of evaluations and follow-up will be monitored periodically throughout the study period and potential problems will be brought to the attention of the study team for discussion and action.

Random sample data quality and protocol compliance audits will be conducted by the study team, at a minimum of two times per year, more frequently if indicated.

16.2 Data and Safety Monitoring

The Data and Safety Monitoring (DSM) Plans at Memorial Sloan Kettering Cancer Center were approved by the National Cancer Institute in September 2001. The plans address the new policies set forth by the NCI in the document entitled "Policy of the National Cancer Institute for Data and Safety Monitoring of Clinical Trials" which can be found at:

<http://cancertrials.nci.nih.gov/researchers/dsm/index.html>. The DSM Plans at MSKCC were established and are monitored by the Office of Clinical Research. The MSKCC Data and Safety Monitoring Plans can be found on the MSKCC Intranet at:

<http://mskweb2.mskcc.org/irb/index.htm>

There are several different mechanisms by which clinical trials are monitored for data, safety and quality. There are institutional processes in place for quality assurance (e.g., protocol monitoring, compliance and data verification audits, therapeutic response, and staff education on clinical research QA) and departmental procedures for quality control, plus there are two institutional committees that are responsible for monitoring the activities of our clinical trials programs. The committees: Data and Safety Monitoring Committee (DSMC) for Phase I and II clinical trials, and the Data and Safety Monitoring Board (DSMB) for Phase III clinical trials, report to the Center's Research Council and Institutional Review Board.

During the protocol development and review process, each protocol will be assessed for its level of risk and degree of monitoring required. Every type of protocol (e.g., NIH sponsored, in-house sponsored, industrial sponsored, NCI cooperative group, etc.) will be addressed and the monitoring procedures will be established at the time of protocol activation.

17.0 PROTECTION OF HUMAN SUBJECTS

Participation in this trial is voluntary. All patients will be required to sign a statement of informed consent, which must conform to MSKCC and collaborating centers IRB guidelines.

Patients will be eligible for this trial regardless of gender or racial/ethnic background. All patients must follow the guidelines for pregnancy testing birth control and counseling related to the risk of fetal exposure to lenalidomide and bortezomib.

The protocol for this study has been designed in accordance with the general ethical principles outlined in the Declaration of Helsinki. The review of this protocol by the IRB and the performance of all aspects of the study, including the methods used for obtaining informed consent, must also be in accordance with principles enunciated in the declaration, as well as ICH Guidelines, Title 21 of the Code of Federal Regulations (CFR), Part 50 Protection of Human Subjects and Part 56 Institutional Review Boards.

17.1 Privacy

MSK's Privacy Office may allow the use and disclosure of protected health information pursuant to a completed and signed Research Authorization form. The use and disclosure of protected health information will be limited to the individuals described in the Research Authorization form. A Research Authorization form must be completed by the Principal Investigator and approved by the IRB and Privacy Board (IRB/PB).

The consent also indicates that samples and genetic information collected may be shared with other qualified researchers. Such information will not include identifying information such as name. It is also stated in the consent and Research Authorization that research data (e.g. genomic sequence) may be placed into databases monitored by the National Institutes of Health, and may be made accessible to investigators approved by the U.S. government.

Consent for re-contact

Patients are asked in a series of check boxes at the end of the consent if 1) if they consent to be contacted to discuss research findings which may derive from their sample; and 2) if not available (e.g. deceased), if they wish to have their designated representative on the consent to be contacted.

Use of identifiable information for genetic studies

It will be explained to participants that future research may also be done to identify changes in genes that predict risk for cancer or other diseases; if such germline genetic research is performed, then to be in compliance with New York State law (see section 3.5), it will not be possible to provide results of research tests not performed in a New York State Department of Health approved clinical laboratory. It is stated in the consent that participants will be told that they will not receive any specific results from potential research tests. The consent will tell participants that if they wish to have genetic testing done for personal reasons than they should make an appointment with the MSKCC Clinical Genetics Service.

If in the course of this research a research finding is obtained that may be critical to the preventive care of the participant or their family, as determined by procedures overseen by the IRB, those participants, if they consent to checklist questions 1, 2, will be referred to the Clinical Genetics Service for a consultation. At that time, genetic counseling can be offered in accordance with New York State requirements, and appropriate clinical testing offered in an

approved laboratory. Please see flow chart and requirements for reporting under section 10.0.

Patients will be informed that future research may also identify changes in genes that predict risks for cancer or other diseases. Procedures for informing patients or their designees, confirmation by a New York State approved laboratory, and followup assessments and counseling are already detailed in Section 10.0 above.

For tumor (somatic) genetic studies, germline studies of genetic variants of unknown significance (e.g. for example, in pharmacogenetics studies), gene discovery studies, and cellular, immunologic, or other studies using banked correlative tissues, the name and personal identifiers may be removed from the sample, but a coded link will be maintained.

Research analysis of tumor genomes may inadvertently reveal, or require some knowledge of the germline genome. Such research studies could be performed on samples not identifiable to the researcher but with identifying links maintained by the TPS, HOTB or similar, and approved via IRB mechanisms. See section 10.0 for instructions on how to report incidental findings on research samples.

Future use of samples

Researchers at MSKCC may either keep indefinitely or dispose of any specimen(s) collected under this protocol including DNA that the samples contain. Specimens will be stored with identifiers in secure banks. Samples could be lost or ruined because of mechanical failure, and MSKCC cannot guarantee that samples will be stored indefinitely. The samples will be stored for as long as deemed useful for research purposes.

Risks of research participation

Risks are those of the procedure to obtain the specimen and are considered minimal. Another risk is release of information from health or research records in a way that violates privacy rights. MSKCC protects records so that name, address, phone number, and any other information that identifies the participant will be kept private and confidential, along with all personal health information.

Benefits of research participation

It is unlikely that the research using biospecimens will be of any medical benefit to participants. Neither the patient nor the treating physician will necessarily be told of the results of any research tests on the samples, except an incidental finding that may be critical to the preventive care of the subject or his/her issue. Research using biospecimens collected in this study could lead to medical and scientific products that could improve prevention, diagnosis, and treatment of disease; but those benefits are unlikely to accrue to the participants.

Occasionally, however, there are tests conducted in research labs, the results of which might contribute toward treatment decisions. These studies would not yet have been reduced to clinical practice, but patients may be informed of such results and how they may affect diagnosis and treatment.

Costs/compensation

There is no cost to enroll or participate in this research. Biospecimens obtained under this research protocol may be used to make secondary products, and such products may be patented or licensed with commercial value. Participants are not financially compensated for use of their human biological specimens or secondary products, tests, and discoveries that derive from their biospecimens.

